10.1.2 Methods for Remote Screening and Enrollment

1. Individuals who are prescreened online and provide contact information will be contacted by a RC/RA within approximately one week of completing prescreening. At this contact, the RC/RA will explain the next steps for screening and enrollment. At this time, the RC/RA will also inquire about whether the patient has an upcoming scheduled appointment with their participating PCP. Refusals and inability to participate will be recorded by the RC/RA in the Participant Tracking Log.
 - a. The patient agrees to continue screening over the phone:
 - i. If the patient does not have an upcoming PCP appointment, the RC/RA will conduct screening, and if eligible, will request permission to obtain electronic consent from the participant for participation. After enrollment,

the RC/RA can continue with baseline activities, including the video doctor and RC/RA-administered assessments, as time allows. The PCP will be asked to follow-up with the patient participant within 10 business days after the baseline to deliver the brief advice. All baseline activities should be completed as soon as possible, preferably within 30 days of prescreening.

- ii. If the patient does have an upcoming PCP appointment in the next 30 days, the RC/RA will conduct screening, and if eligible, will request permission to obtain electronic consent from the participant for participation prior to their PCP appointment. The RC/RA should wait to enroll the participant and conduct the rest of the baseline activities until after the PCP appointment. If the patient misses or reschedules their PCP appointment, then the RC/RA can complete baseline activities and ask the PCP to follow-up to provide brief advice within 10 business days of the baseline visit.
- b. The patient does not want to continue with remote screening and provide consent:
 - i. If the patient does not have an upcoming PCP appointment in the next 30 days, the RC/RA will schedule another time within the 30 day screening window (either in-person or remote) to continue screening and if eligible, complete enrollment procedures. Once enrolled, the RC/RA can continue with the baseline activities (video doctor and RC/RA-administered assessments). The PCP will be asked to follow-up with the patient participant within 10 business days after the baseline to deliver the brief advice.
 - ii. If the patient does have an upcoming PCP appointment in the next 30 days, the patient will be instructed to arrive to their appointment 30 minutes early to conduct screening, and if eligible, provide consent for participation before seeing their provider. The RC/RA should wait to enroll the participant and conduct the rest of the baseline activities until after the PCP appointment. If the patient misses or reschedules their PCP appointment, then the RC/RA can complete baseline activities and ask the PCP to follow-up to provide brief advice within 10 business days of the baseline visit.
- c. Patients who prescreen eligible, but screen ineligible are not eligible to participate in the study. If they screen ineligible due to moderate or severe OUD or receipt of MOUD, the RC/RA will provide the patient with overdose prevention information (including printed and/or electronic materials); a list of community and/or clinic resources for OUD treatment; contact information for a social worker or behavioral health staff in the patients clinic, if available; an ineligible patient letter patients can provide to their PCP (for moderate to severe OUD patients only); and will suggest that patients speak with their primary care provider.

2. Individuals who prescreen eligible and contact the RC/RA themselves will follow the same process outlined above for a) remote screening and consent, b) in-clinic screening and consent, or c) ineligible status.
3. If a prescreened eligible patient has an upcoming PCP appointment, but is not reached by the RC/RA prior to their PCP appointment, the patient can complete screening and consent any time within 30 days of prescreening.
4. Individuals who prescreen eligible but are not screened by the RC/RA within 30 days, will need to begin the process for determining eligibility again after the 30 day window. Please refer to the MOP for additional details and Section 10.2.2 for consent procedures.

10.1.3 Methods for In-Person Prescreening, Screening and Enrollment

[figure not shown]
1. RC/RAs will approach patients in the clinic and follow the RC/RA in-clinic recruitment script. They will then offer patients the prescreening questionnaire on a tablet if they have not already completed it (in the past 30 days). Assistance may be provided by the RC/RA if this is requested by the patient. If the patient is not able or willing to use the tablet, paper CRFs will be available. All paper assessments will be stored as source documentation. Patients with prescreening results indicating that they may be eligible for participation in the study will be informed of this by the RA, who will meet with them in a private area to conduct screening, and if eligible obtain consent. Enrollment procedures and baseline activities can continue after the PCP appointment, as needed, or preferably within 30 days of prescreening.
2. If an individual screens ineligible due to moderate or severe OUD or receipt of MOUD the RC/RA will provide the patient with overdose prevention information (including printed and/or electronic materials); a list of community and/or clinic resources for OUD treatment; contact information for a social worker or behavioral health staff in the patients clinic, if available; an ineligible patient letter patients can provide to their PCP (for moderate to severe OUD patients only); and will suggest that patients speak with their primary care provider.

10.1.4 Methods for Telehealth Prescreening, Screening and Enrollment

1. If a patient completes the prescreener prior to a telehealth visit, the RC/RA will attempt to reach out to them prior to the telehealth visit and conduct screening and consent. If eligible and the patient enrolls in the study, the RC/RA will provide the patient's PCP with the patient's screening results as indicated in the local SOP.
2. If a patient does not complete the prescreener prior to their telehealth visit, the RC/RA may call the patient prior to their scheduled telehealth visit to inquire about their interest in participating. If a patient is interested, the RC/RA will text or email the prescreener survey to the patient, and either stay on the phone with the patient as they complete it or have the patient call them back when finished.
 - a. If the patient is ineligible, the RC/RA will thank them for their time using an IRB approved script.

- b. If the patient's prescreening results indicate that they may be eligible, the RC/RA will conduct screening, and if eligible obtain consent.
- c. If an individual screens ineligible due to moderate or severe OUD or receipt of MOUD, the RC/RA will provide the patient with overdose prevention information (including printed and/or electronic materials); a list of community and/or clinic resources for OUD treatment; contact information for a social worker or behavioral health staff in the patients clinic, if available; an ineligible patient letter patients can provide to their PCP (for moderate to severe OUD patients only); and will suggest that patients speak with their primary care provider.

Figure 4: Patient Prescreening and Enrollment

*If a patient has a PCP appointment and there is not enough time to read the full study consent before their PCP visit, the RC/RA may obtain verbal consent instead using a brief IRB approved consent script. In such cases, patients will read and sign the full consent after their PCP visit.

**Research staff are encouraged to complete the baseline visit as soon as possible after enrollment, preferably within 30 days of prescreening.

10.2 Prescreening and Assessment of Study Eligibility

The prescreener will include tools to assess study eligibility and a general health behavior questionnaire called the “healthy living survey,” which includes questions about general health behavior (exercise, diet) as well as substance use. The purpose of including questions that are not about substance use is to partially mask the topic of the study for potential participants, and those questions will not be used to determine eligibility. For all patients, the prescreening tool includes the Tobacco, Alcohol, Prescription medication, and other Substance Screening Tool (TAPS Tool). The TAPS Tool is a brief screening and assessment instrument that was developed and validated in CTN-0059. For patients who have received a prescription for opioid medication in the 6 months prior to date of prescreening, based on patient self-report, the prescreening tool will additionally include the Current Opioid Misuse Measure (COMM).[43, 44] The study will utilize three items from the COMM, items 9, 14, and 15, to determine eligibility. Prior to each of these three questions, there will be an instruction line informing patients that the questions are only asking about their opioid pain medications.

Prescreening is considered positive if the patient has a TAPS score ≥ 1 for heroin and/or prescription opioids, and/or a positive response to COMM items 9, 14, or 15. The TAPS Tool requires at least 1 day of unhealthy opioid use in the past 90 days to achieve a score of ≥ 1 , and the COMM requires opioid misuse behaviors to have occurred in the past 30 days.

Individuals with a positive prescreen for risky opioid use, but do not meet the other eligibility criteria, will receive from the RC/RA additional information about overdose prevention and OUD treatment. This may include specific information about linkage to clinic resources that can assist them with initiating MOUD treatment, as detailed in the MOP and site specific standard operating procedures (SOPs).

Prescreening forms will not include identifying information for those who are ineligible; however, if a patient prescreens eligible, they will be asked to create a unique ID (referred to as ‘study ID’ in patient participant facing materials) and leave their contact information for the RC/RA to reach them. Individuals who are interested and screen eligible will undergo the informed consent process described below. Patients who do not qualify for the study will receive no further intervention, but the anonymous prescreening data will be kept to allow comparison to those who do qualify.

Because the prescreener is anonymous, the research staff will not know who has already completed it. Therefore, patients may receive an invitation to take the prescreener more than once, but they will be instructed to not complete it more than once in a 30 day period.

10.2.1 Screening for Eligibility

Patients who are interested in enrolling and have prescreening results suggesting study eligibility will meet with research staff by phone or in-person in a private area of the clinic, to complete the information needed for assessment of eligibility. Research staff will administer the CIDI opioid items and complete a checklist of inclusion/exclusion criteria to make a final determination of eligibility for enrollment. If the screener assesses that the patient is eligible, they can move onto informed consent and enrollment.

Patients who prescreen eligible but screen ineligible, may receive another invitation to reinitiate the prescreening and screening process, but should be encouraged not to take the prescreener more than once every 30 days.

10.2.2 Informed Consent Procedures

The study includes PCPs and patients as participants. All participants will give informed consent for study participation.

Informed Consent for PCP Participants

PCPs will be recruited and enrolled prior to the enrollment of patients (see recruitment of PCPs, Section 8.2.1). Those who are eligible will be provided with an IRB-approved informed consent form on paper and/or electronically and will be asked to sign this document. The study investigators will not inform personnel outside of the study whether providers have chosen to participate and if so, to which group they have been randomized. PCPs will be allowed to inform others about their participation, if they choose to.

Informed Consent for Patient Participants

Patients are not informed of the PCP's study intervention assignment prior to enrollment. They are informed that their PCP is participating in a healthy living study and that they will receive either the STOP intervention elements (including nurse care manager, telephone health coaching) or EUC. Screening, enrollment, and consent can be completed any time within 30 days of prescreening eligible.

Informed consent will be obtained from patients before their baseline visit using an IRB-approved informed consent form on paper and/or electronically. A brief verbal consent will be available as a backup for patients enrolling before a PCP appointment who do not have time to read and discuss the full consent form before their PCP appointment. In such cases, patients will be read an IRB-approved verbal consent script and will be asked to provide verbal consent for participation in all study activities that take place during the PCP appointment (PCP brief advice and/or video doctor). Following the PCP appointment, and prior to completion of the baseline assessments, these individuals will sign the full consent which covers participation in all study activities. Consent forms will be in compliance with the pertinent sections of 45 CFR 46. Because of the low risks associated with the study, the consent form will be as brief as possible within the constraints of adequate human subjects protections. The consent form will include a description of all significant elements of the study. We also will obtain permission to audio record some telephone health coaching sessions for intervention fidelity monitoring purposes. Given the multi-site nature of the trial, it is possible that ancillary studies will be proposed before or after the study begins recruitment. For this reason, during the informed consent process, we also will seek permission to contact the participant in the future about other study opportunities.

Research staff will be available to answer questions about the consent form while patients are reviewing the document. Patients will read the informed consent document (or have it read to them, if this is preferred) and express verbally their understanding of the key elements of the study (e.g., description of the treatment condition, duration of follow-up). They then indicate their

consent to participate in the study by signing (either written or electronic) the informed consent form.

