10.6.1 Enhanced Usual Care (EUC)

In the **EUC arm**, PCPs will conduct primary care as usual, without the support of the NCM. At the baseline visit, patient participants receive educational materials and view a short video. The educational materials include information about preventing opioid-related overdose, including how to obtain a naloxone kit; and a handout on cancer prevention. The video content will feature information on cancer prevention. It will be viewed on a tablet or desktop computer and will be approximately 2 minutes long. All EUC patient participants receive the same video, which is not tailored to the responses given on their questionnaires. There is no study intervention after the baseline visit.

There are no limitations placed on primary care treatment as usual. The EUC condition enhances usual care by providing patient participants with an OD prevention educational handout. This is done for safety reasons, because the current standard of care in most primary care clinics is to offer no universal screening for opioid use or OD prevention interventions in primary care. The local research teams at each site will ensure that information on naloxone is detailed and specific, and that the pamphlet gives clear guidance on how to access naloxone. The content will be further detailed in the manual of procedures and/or site standard operating procedures.

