Video Doctor: The video doctor should be completed as part of the baseline visit. If the patient participant sees their PCP during the baseline visit, they will view the Video Doctor after they see their PCP and before they complete the baseline assessments. If the patient participant does not see their PCP as part of the baseline visit, the RC/RA will show them the Video Doctor after consent and enrollment. For telehealth or remote visits, the video link may be sent via email or text to the patient participants. The video is a recording of a provider delivering brief advice about opioid use that includes the same elements covered in the summary report outlined above, and will be specific to use of illicit or prescribed opioids. The video may also include an introductory message from the site NCM and the telephone health coach(es).

Patient participants in the STOP intervention will receive an educational pamphlet, which includes information about preventing opioid-related overdose, including how to obtain a naloxone kit. Patient participants will also receive a printed handout with information about the NCM and telephone health coaching sessions, including the benefits and expectations of their participation, schedule of research visits and telephone health coaching sessions, and contact information. When possible, the NCM will introduce themselves to the patient participant in-person during the course of the baseline visit. The NCM may reach out to the patient participant following the baseline visit (by phone, email, text message, or via the patient portal) to introduce themselves.

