10.10 Blinding

10.10.1 Type of Blinding

Randomization is at the level of the PCP, and PCPs will be aware of their assignment to the STOP vs. EUC condition. NCMs and telephone health coaches will only interact with patient participants in the intervention condition and will not be informed about patient participants who are enrolled in the EUC condition or who are not participating in the study. Patient participants are blinded to the treatment condition of their PCP and will be informed that the purpose of the research is to study health behaviors, not limited to opioid use.

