10.10.2 Maintenance of the Blind

Most assessments are self-administered (SA) by patient participants. It is not feasible to blind research staff because the delivery of some intervention components require their involvement (e.g., showing educational video vs. video doctor to the participant, intervention specific CRFs). Patient participants may be able to deduce the assignment of their PCP, (e.g., through conversation with other patient participants in the study), but this information will not be

volunteered by clinical or research staff. To assess the success of the blind, patient participants will be asked at the end of the study what they considered to be the goal of the research.

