11.6.3 Patient Experience Questionnaire

A self-reported questionnaire will collect information from patient participants about their interactions with care providers in the past 3 months. Individuals assigned to the STOP intervention will complete all items of the questionnaire (pertaining to PCP, nurse care manager, and telephone health coach), while individuals assigned to EUC will complete only the PCP section. The questionnaire addresses the ‘individual’ level of influence in our conceptual model by assessing patient satisfaction and comfort with the patient-facing intervention components. For participants who report receipt of opioid counseling, they will complete additional items about how they perceived the counseling in relation to the reason they sought care, how helpful it was to them, what they learned, and if it made them think about changing their opioid use behavior. The questionnaire is administered with the quarterly assessments at months 3, 6, 9, and 12. Because the telephone health coaching intervention ends by month 6, the telephone health coach-specific items are not administered in the month 9 and month 12 assessments.

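### Patients are described as blinded to arm, but consent names STOP components that then visibly arrive or do not, and the planned check asks about the study's topic rather than the arm

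*Protocol*

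**What the plan says.** **Blinding claim.** Protocol 10.10.1 says: "Patient participants are blinded to the treatment condition of their PCP". SAP 2.3.4 repeats it, and Protocol 2.1.1 and SAP 2.1 say the same. Protocol 10.10.2 adds that research staff cannot be blinded, that staff will not volunteer the assignment, and that patients might work it out. Its example is talk with other participants.

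**Consent (Protocol 10.2.2).** "Patients are not informed of the PCP's study intervention assignment prior to enrollment". They are nevertheless told that "they will receive either the STOP intervention elements (including nurse care manager, telephone health coaching) or EUC", and "The consent form will include a description of all significant elements of the study".

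**What follows.** In STOP (10.6.2): "Patient participants will also receive a printed handout with information about the NCM and telephone health coaching sessions". Coaching is offered at about weeks 2 and 4. In EUC (10.6.1), patients receive a video and printed materials at baseline, and then: "There is no study intervention after the baseline visit". From month 3 the experience questionnaire (11.6.3) has nurse and coach items for STOP patients, while "individuals assigned to EUC will complete only the PCP section".

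**Check of the blind.** Protocol 10.10.2: "patient participants will be asked at the end of the study what they considered to be the goal of the research". The answer categories in 11.7.2 are all study topics (opioids, drugs or alcohol, exercise, weight loss, healthy lifestyle, other).

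**Outcome.** The primary outcome is the sum of six monthly self-reports, and SAP 7.2.1 admits no other data source. SAP 7.8 tabulates urine screens by arm and by opioid prescription but excludes them from the primary analysis.

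**The concern.** Two different kinds of masking sit under one label. The study does try to hide its opioid focus, by presenting itself as a study of general health behaviour. Hiding which intervention a patient is getting is another matter: consent has already named the nurse and the coach, and from baseline a patient can see whether they appear.

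This matters because the outcome is what patients say about their own risky opioid use, and STOP patients are advised to reduce that risk. If reporting shifts more in STOP than in EUC, fewer reported days need not mean fewer days of use. A report that calls patients blinded, supported by a check that looks successful, would invite readers to discount that possibility on evidence that does not bear on it.

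**Working it through.** The point is textual. The arithmetic in step 4 only illustrates what could be at stake.

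**1. What a patient can compare**

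| Moment | STOP | EUC |
|---|---|---|
| Consent (10.2.2) | Told: nurse and coaching, or EUC | Same |
| Baseline (10.6.1, 10.6.2) | Handout naming nurse and coaching; opioid advice video | Overdose and cancer-prevention materials; cancer-prevention video |
| Weeks 2 and 4 | Coaching calls offered | Nothing |
| Month 3 onward (11.6.3) | Nurse and coach items | PCP items only |

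The route to the arm is the consent wording set against the care received. It needs no contact with other patients, which is the only route that 10.10.2 gives as an example.

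**2. Timing against the outcome.** Baseline days of use come from the prescreening survey (SAP 3.3.4), before consent. The outcome surveys fall at days 30, 60, 90, 120, 150 and 180. Coaching targets are days 2 × 7 = 14 and 4 × 7 = 28. Attempts may run three weeks longer, to days 14 + 21 = 35 and 28 + 21 = 49. So all six surveys follow the baseline handout. The first survey may precede coaching for some patients; from day 60 both windows have closed. The baseline covariate precedes any arm knowledge, and every component of the outcome follows the first cue.

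**3. What the check can show.** A STOP patient who knows they have the nurse and coach can truthfully answer that this was a healthy lifestyle study. So can an EUC patient who has noticed that neither appeared. Both would count as successful blinding. A difference in answers between arms would be only an indirect hint, because STOP patients hear opioid-specific advice whether or not they can name their arm. Section 11.7.2 places the item at 12 months or the last visit, while Protocol Table 6 appears to mark 6 and 12 months (the layout may have suffered in extraction). The output list in SAP 17.0 contains nothing for it.

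**4. Illustration.** Inputs from Protocol 14.5 and SAP 10.0: binomial counts out of 90 for each of two intervals, control mean 20 per interval (nominally 40 per 180 days), PCP variance 0.15, individual variance 0.25, 20% dropout, and a negative binomial model with random PCP intercepts. Variances were placed on the logit scale, which is an assumption.

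The plan's own figure comes first. Scenario 1 is 40 against 28 days, a ratio of 28/40 = 0.70, with stated power 0.97 (60 PCPs × 5 patients) and 0.93 (50 × 4). With the individual intercept redrawn for each interval, 300 runs gave 0.98 and 0.93. With one intercept per patient they gave 0.91 and 0.88, below the stated values. The documents do not say which was used.

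Now assume no true effect, 60 × 5, and STOP patients alone omitting a fraction *f* of use days. The reported STOP mean is 40 × (1 − *f*). Rejection rates use the one-intercept version:

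| *f* | Reported means, STOP vs EUC | Ratio | Negative binomial model, 300 runs | Cluster t-test on log means, 4,000 runs |
|---|---|---|---|---|
| 0 | 40 vs 40 | 1.00 | 6% | 5% |
| 5% | 38 vs 40 | 0.95 | not run | 9% |
| 10% | 36 vs 40 | 0.90 | 25% | 20% |
| 15% | 34 vs 40 | 0.85 | 46% | 42% |
| 20% | 32 vs 40 | 0.80 | 71% | 68% |
| 30% | 28 vs 40 | 0.70 | not run | 97% |

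The Monte Carlo standard error at 300 runs is at most √(0.5 × 0.5/300) = 0.029. Because the one-intercept version has lower power than the plan states, these rates are, if anything, on the low side for a given *f*.

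**The case against.** **The protocol partly concedes the point.** Section 10.10.2 admits that staff are unblinded and that patients may infer their assignment, and 10.10.1 describes masking of purpose, which the goal question fits. That is fair. But the unqualified blinding statements remain in four sections, and the concession omits the main route.

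**There are safeguards.** Substance-use surveys are self-administered to limit social desirability bias (6.1), and urine is collected at baseline, 6 and 12 months to verify self-report. These count. Self-administration, however, does not address reporting that differs by arm. Counts of positive screens by arm do not link a patient's report to that patient's sample, and the SAP specifies no concordance analysis. Protocol 6.1 itself says biological tests miss intermittent use and overuse of one's own prescription.

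**A reader might infer that blinding does not exist and that every STOP patient knew the arm.** The documents do not support that. Consent names EUC without listing its contents in 10.2.2, the form itself is not available here, both arms receive a video and printed materials, coaching may be declined, and later nurse outreach is optional. How many patients worked out their arm is unknown.

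**Knowing the arm is not the only mechanism.** Being advised to cut down may change reporting even in a patient who could not name the arm. This objection stands. It means a perceived-arm question alone would not separate less use from less reporting.

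**Conclusion.** The concern holds in a limited form. Patients are not told their assignment and are partially masked to the opioid focus, but blinding to arm cannot be relied on once STOP contact begins or fails to begin. The check of the blind measures masking of purpose and cannot show knowledge of arm. This rests on comparing the protocol's own sections, not on a calculation, and no figure in either document is wrong on this point.

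The size of any bias is unknown because the documents give no under-reporting rate. The rejection rates above are conditional on assumed fractions. They show that modest differential reporting would matter for this endpoint, with 30% matching the whole planned ratio of 0.70. A reader might take them as evidence that the primary result is biased; they are not. The point calls for accurate description and two supporting tables, and it does not invalidate the primary analysis.

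**What to change.** 1. In Protocol 2.1.1 and 10.10 and SAP 2.1 and 2.3.4, state that patients are partially masked to the opioid focus and not told their assignment, but are not reliably blinded to the intervention received, so the primary outcome is effectively unblinded self-report.
2. In Protocol 10.10.2 and 11.7.2, describe the goal question as a check of masking to study purpose, and reconcile its timing with Table 6.
3. Add two SAP tables: goal answers by arm, and self-report against urine screen concordance by arm at baseline, 6 and 12 months. Split the second by opioid prescription, as SAP Table 64 already does, since a positive screen in a patient with a prescription does not contradict a report of no risky use. Note what urine cannot detect.
4. Only if data collection is still open, add one perceived-arm item to the existing form. That looks unlikely: Protocol 14.5.4 had 12 months of enrolment left in November 2021, and a further 12 months of follow-up leads to about November 2023, while SAP version 2.0 is dated May 2025.

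The cost is some wording, two tables from data already planned for collection, and a less favourable blinding statement. The primary model and sample size do not change.
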